**1. TITLE**

*A Pilot and Feasibility Study to Promote Physical and Food Literacy among Children with Intellectual Disabilities (Study Nickname: New Skills – No Scores)*

**2. EXTERNAL IRB REVIEW HISTORY\***

UMass Chan will be the lead institution and reliance agreements have been put in place with Tufts University and UMass Boston.

**3. PRIOR APPROVALS: N/A****4. OBJECTIVES\***

The specific aims of the study are as follows:

- (1) To test the feasibility of a remote physical literacy and food literacy intervention for adolescents with ID ages 12-16 years.
- (2) To assess preliminary efficacy of the intervention for increasing:
  - a) physical literacy including movement skills, physical self-concept, and desire to participate in physical activity.
  - b) food literacy including knowledge around making healthy food choices, basic food preparation skills, and engaging in healthy eating behavior.

We hypothesize that demand for the intervention will be similar to our previous studies (high level of interest), and attendance and retention will be high ( $\leq 10\%$  dropout). We also hypothesize that participants will enjoy the intervention, and that parents and participants will be satisfied with the intervention and perceive it as appropriate. We expect that implementation fidelity will be high ( $> 80\%$  of checklist items on average) and that participants will show significant improvements in physical literacy and food literacy outcomes. This pilot and feasibility study represents an important first step toward promoting health and reducing inequities that exist for adolescents with ID. If successful, the next step is a larger controlled study to test whether changes in physical literacy and food literacy skills can promote increased physical activity and healthier food choices in adolescents with ID.

**5. BACKGROUND\***

This information described extensively in the grant narrative that has been uploaded into the eIRB system. Below is a brief description of the background/context for the study:

Regular participation in physical activity (PA) maintains health and reduces the risk of disease. In children and youth, benefits include improved blood pressure, bone health, 4 health-related fitness, psychological health, and preventing/treating obesity. The US guidelines for children recommend at least 60 min/day of moderate-to-vigorous activity but less than 25% children meet this goal. PA levels are lower in girls than boys, and decline from childhood to adolescence. 53 Children with intellectual disabilities (ID) are no exception; most do not meet

the guidelines and are less active than their typically developing (TD) peers. A healthy diet is also necessary for overall health and well-being. The Dietary Guidelines for Americans are promulgated to help people make healthy food and beverage choices. Data from the 2015 Youth Risk Behavior Surveillance Survey suggest that a substantial number of youth do not meet these guidelines; only 61% of high school youth consumed  $\geq 1$  vegetables and only 63% consumed  $\geq 1$  servings of fruit or 100% fruit juice daily. Although data on dietary intake of children and youth with ID are lacking, our work in youth with ID suggests that many do not meet the dietary guidelines for fruits/vegetable intake and that their diets are high in added sugars. Barriers to healthy eating include lack of knowledge about food in today's complex food environment which makes decision-making around food choices difficult. Other barriers include difficulty estimating portions sizes, food selectivity, and limited of access to healthy foods.

The concept of physical literacy has gained considerable momentum internationally in health promotion research, practice, and policy. The International Physical Literacy Association describes physical literacy as “the motivation, confidence, physical competence, knowledge and understanding to value and take responsibility for engagement in physical activities for life.” It imparts the knowledge and tools to pursue and enjoy a variety of sports and PA. Physical literacy is considered the gateway to an active lifestyle. In the US, the physical literacy movement is embraced by organizations like the American College of Sports Medicine and President’s Council on Fitness, Sports & Nutrition. In 2014, “physically literate” replaced “physically educated” as the goal for all students in the US National Standards for Physical Education.

The essential components of physical literacy, in the US definition, are:

- 1) Ability: competency in basic movement skills and overall fitness;
- 2) Confidence: self-efficacy for the ability to play sports or enjoy physical activities; and
- 3) Desire: the intrinsic enthusiasm for PA.

These components build on one another and provide the foundation to be active for life. Specifically, as children develop proficiency in movement skills, their increased confidence in their ability leads to greater enjoyment and motivation to participate. Mastering fundamental movement skills such as jumping, running, catching, and throwing is considered to be the most important step toward developing physical literacy. Children and adolescents with more developed motor skills are more active/fit, which enhances movement proficiency and increases overall activity levels.

Food literacy has also gained recent attention and has been defined as “the capacity to obtain, process and understand basic information about food and nutrition as well as the competence to use that information in order to make appropriate health decisions,” although a standard definition of this concept is not yet established. A food literacy intervention for adolescents with ID must consider the adaptations needed to make information accessible and understandable, teach skills that are reasonable and manageable, and meet the needs of a heterogeneous population. The range of knowledge in adolescents with ID is likely to be quite variable. Although adolescents with ID may live in supervised settings or at home with their parents, they nevertheless make food choices throughout their day. Thus, they need to be able to identify healthy food choices and be able to identify unhealthy foods which are often the targets of marketing and advertising. Moreover, adolescents with ID have higher rates of food selectivity

than their TD peers, which may be a result of sensory sensitivities, behavioral rigidity, and/or preferences for familiar foods. These adolescents need to be exposed to healthy foods in a positive and supportive manner. Food literacy is critical to the health of adolescents with ID who require requisite knowledge and skills for making healthy choices, especially as they move toward more independent living.

## **6. INCLUSION AND EXCLUSION CRITERIA\***

The participants in this study will be 30 male (n=15) and female (n=15) adolescents with intellectual disabilities (ID) ages 12-16 years. Because the etiology of ID is variable with many known and unknown causes, we expect the sample will include adolescents with various syndromes such as Down syndrome, Fragile X, Williams syndrome, as well as adolescents with ID of unknown etiology.

Inclusion criteria:

- measured IQ and adaptive functioning scores of  $\leq 75$  as measured by the Kaufman Brief Intelligence Test-2 (KBIT-2) and Vineland Adaptive Behavior Scales-III (VABS-III). A score  $> 75$  for participants that do not have a syndrome that is associated with ID will be exclusionary. However, participants with such syndromes (e.g., Down syndrome) may have scores above this cut-point but are still classified as having an intellectual disability and thus will qualify for the study.
- participants must be ambulatory and in sufficiently good health to engage in moderate-to-vigorous physical activity
- able to communicate verbally in English, follow simple instructions, and provide assent.
- approval from the participants' primary care physician and specialists (as necessary) will be required for participation.
- in-home space that is a minimum of 7 feet by 10 feet to allow the participant enough room to complete the TGMD-3 and the physical activity component of the intervention

Exclusion criteria:

- uncontrolled medical or significant psychiatric condition
- insulin-dependent diabetes
- physical/orthopedic impairment that would preclude participation in physical activity
- legally blind or deaf
- habitual problem behaviors such as aggression or noncompliance

We will seek approval from participants' physicians and specialists to ensure they can participate safely.

## **7. STUDY-WIDE NUMBER OF SUBJECTS\* N/A**

## **8. STUDY-WIDE RECRUITMENT METHODS\* N/A**

## **9. STUDY TIMELINES\***

The table on the next page depicts study activities over the two years of the project. The 12-week intervention will run remotely in three concurrent waves/cohorts of 10 participants (winter/spring 2022 through summer 2022). Conducting the intervention remotely will allow us to recruit

throughout the state of Massachusetts, which will assist in enrolling the planned number of participants (n=30).

The study was put on-hold in March 2020 due to COVID shortly after enrolling participants and commencing with the intervention. The timeline listed below illustrates our new plan.

		Year 2 Sept 1 2020 to Aug 31 2021												Year 3 – Current Year (no-cost extension) Sept 1 2021 to Aug 31 2022												
Tasks ↓	Months ⇌	S	O	N	D	J	F	M	A	M	J	J	A	S	O	N	D	J	F	M	A	M	J	J	A	
Participant-related activities suspended due to COVID-19		X	X	X	X	XX	X	X	X	X	X	X	X													
Start-up activities – hire staff, training and preparation														X	X	X	X									
Recruit, screen, & enroll participants																	X	X	X							
Data collection – baseline measures																	X	X	X							
Intervention																				X	X	X	X			
Data collection – post intervention measures																									X	
Data coding, entry & analysis																									X	X
Dissemination - presentation and manuscript preparation.																										X

## **10. STUDY ENDPOINTS\***

The measures used in this project are designed to test the feasibility of the intervention and assess its preliminary efficacy for increasing physical literacy and food literacy in adolescents with ID. Measures of physical literacy and food literacy will be obtained **at baseline and after the 12-week intervention.**

Below are brief descriptions of the measures – these are also described in the grant application, which includes bibliographic references for validated measures.

### **(1) General sample characterization**

We will collect the following information at baseline to characterize the sample:

- **Demographic Questionnaire.** Parents will be asked to complete a demographic questionnaire that contains basic demographic questions about the adolescent's date of birth, sex, adolescent/family race/ethnicity, and parent education. This questionnaire also contains questions about individual, social, community, and family barriers to physical activity for the adolescent.

### **(2) Feasibility Measures**

Process measures of demand, acceptability, and implementation will be obtained as follows:

- *Demand* will be assessed by documenting number of inquiries into the program and number of participants screened and enrolled. Attendance will be recorded for each session and we will document reasons for any absences. Withdrawal, date of withdrawal, and reasons will also be documented.
- *Acceptability* will be assessed via participant and parent surveys of enjoyment, satisfaction, and perceived appropriateness at weeks 6 and 12. Surveys will be adapted from those used in our previous work, and will include close-ended questions with Likert scale response options and opportunities for open-ended feedback. The participant survey will be simple and will include visual cues (e.g., happy face for “like it”) to assist in understanding questions and response choices. The survey will be administered orally and will take about 15 minutes. Participants will be queried about program elements such as: appropriateness and enjoyment of the sport/healthy eating activities; sports equipment; support/instructional methods used by staff; using Zoom to conduct the intervention remotely; barriers/facilitators of participation in physical activity and healthy eating; enjoyment of interactions with other adolescents; preferred sports and taste test foods; perceived improvements in physical/food literacy; and enjoyment/perceptions of “*Bring it Home and Give it a Try*” activities. Parent satisfaction via a survey will query perceptions such as: program quality; benefits to adolescent; staff effectiveness; appropriateness of activities; adolescent enjoyment; quality of the facility; and barriers to/facilitators of participation.
- *Implementation* will be assessed via documenting the factors affecting program implementation and sufficiency of resources (e.g., space, staff), and fidelity checks. Through observation and discussions with staff, participants, and parents, we will document: adaptations made to increase success; effective/ineffective strategies used to promote participation; most appropriate sports; quality of activity sessions; and barriers and facilitators encountered. Fidelity checks will be conducted in 25% of the program

sessions starting in week 3 to assess the degree to which the intervention is implemented as planned. We will develop a checklist with critical elements of the program and will discretely observe and record if the elements are executed. Protocol “violations” will be recorded and brought to the investigative team for discussion and trouble-shooting. In addition, we will have all active staff complete a Field Notes form at the end of each session to note any challenges with the session and/or participants. While these forms will have participant names on them they will be stored in a locked box after the session and brought de-identified as soon as possible by redacting the name and adding the subject ID instead.

- *Session Observation Form:* The Session Observation Form will be completed by nutrition students who will be involved in the intervention. During and immediately following the session they will take notes and fill out the form in order to capture aspects of program implementation. This form will assist us to evaluate the feasibility of and participant engagement with the program.

### **(3) Measures of Physical Literacy**

- *Movement Skills.* **Test of Gross Motor Development-Third Edition (TGMD-3)** will be used to measure movement skills. The TGMD-3 assesses 13 fundamental motor skills that are divided into two sub-scales: 1) locomotor skills and 2) ball skills. The TGMD-3 is a direct observation skill assessment with 3-5 performance criteria for each skill. The following skills from the TGMD-3 will be assessed: skipping, two-foot jumping, one-foot hopping, sideways sliding, overhand throw, underhand throw, catch, hand dribble, and kick. The TGMD-3 will be administered via Zoom (i.e., remotely) at baseline and post-12 weeks. Specifically, a trained tester will provide verbal instructions and demonstrations for each skill on the TGMD during a recorded Zoom meeting. A parent/guardian will assist by ensuring that the participant’s performance is clearly visible in the frame of the camera and may provide prompting and/or clarification to their child. Additionally, instructional videos for each TGMD skill will be provided to the participants and parents in advance for them to review and practice before the testing session. It should take approximately 30-40 minutes to administer. A trained professional will review and code the video-recorded TGMD-3 performance on each skill and provide a score at baseline and post-test.
- *Motivation and Confidence in Physical Activity.* As an indicator of confidence, Physical Self-Concept will be measured using the **Very Short Form of the Physical Self-Inventory-Intellectual Disability (PSI-VSF-ID)**. The PSI-VSF-ID is simple, accommodates short attention span, and assesses the multidimensionality of physical self-concept. The PSI-VSF-ID has 12 items that measure six dimensions of self-concept: 1) Global Self-Concept; 2) Physical Self-Worth; 3) Sport Competence; 4) Physical Attractiveness; 5) Physical Condition; and 6) Physical Strength. We have modified the language of the items of the PSI-VSF-ID for clarity and understanding by children with ID based on our extensive experience with this population. The 3-item confidence subscale, and 3-item motivation subscale of the **Canadian Assessment of Physical Literacy – Second Edition (CAPL-2) Questionnaire** will also be used to assess participant confidence in their ability to be physically active and motivation to participate in physical activity. This combined 18-item questionnaire including the PSI-VSF-ID and CAPL-2 subscales will be verbally administered virtually over Zoom. We reduced the

number of response options to four to accommodate children with ID who may find 5 or 6 choices difficult, and modified the language so that there was consistency across all of the 18 items in the combined motivation and confidence questionnaire. The response options are simply-worded for children with ID, and range from “yes, definitely” to “no, definitely not”.

- *Desire to Participate in Physical Activity.* The adequacy and predilection for physical activity subscale of the **Canadian Assessment of Physical Literacy – Second Edition (CAPL-2) Questionnaire** will estimate the participant’s desire to participate in physical activity. The 6-item questionnaire subscale includes 3 items that assess perceived adequacy (i.e., self-perception that one has the capability to achieve an acceptable standard of success conceptualized by the self and others) and 3 items that assess perceived predilection for physical activity (i.e., likelihood of selecting physical activity over sedentary behavior when given the choice). This shortened and refined version of the original CAPL Questionnaire is underpinned by self-determination theory which is often used to understand motivation and perceived competence (Gunnell et al., 2018). The adequacy and predilection subscale, called “What’s Most Like Me?”, uses an alternative response choice format to present statements about preferences and feelings about physical activities and an adolescent chooses the option that is most like them. For example, “some kids don’t have much fun playing sports” and “other kids have a good time playing sports.” We have modified the response items to ask participants to select which option is most like them. The CAPL-2 Questionnaire subscale will be verbally administered virtually over Zoom. Total scores will range from 0-6 with an item response assigned 0 or 1.

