## **12. DATA AND SPECIMEN BANKING\* N/A**

### **13. Data Analysis and Management\***

All data will be double entered and linked by a common identification number across data sources. We will minimize missing data through careful checking of all surveys and data forms at the time of completion. Baseline characteristics of participants who drop out will be compared to those who complete the study.

Analyses for Specific Aim #1. The process measures of feasibility will assess attendance, degree of participant enjoyment, and participant and parental satisfaction based the aforementioned surveys. These measures will be summarized as means and proportions, with corresponding 95% confidence intervals, and compared across the two waves. If there are no important differences, we will pool across waves. We will use the 6-week and 12-week measures to assess if engagement builds, sustains or declines over the intervention period. We will also examine study completion and attendance by wave.

Analyses for Specific Aim #2a. To assess if the intervention increases aspects of physical literacy including movement competence (ability), confidence, and desire to participate in physical activity, we will conduct 1-sample paired t-tests for change (against the null hypothesis of a change of zero) in separate tests for TGMD-3 scores, PSI-VSF-ID physical self-concept, and CSAPPA score. We will construct 95% confidence intervals around the measure of change separately for boys and girls, and pool them if we discern no important differences by sex. If, based on Aim #1, we believe there were important implementation differences between the two waves, we will analyze them separately, acknowledging our power will be more limited.

Analyses for Specific Aim #2b. Analyses to assess if the intervention increases elements of food literacy (i.e., knowledge and skills) for promoting intake of fruits and vegetables and for decreasing intake of high energy low nutrient dense snack foods will proceed as for Aim #2a. We will use a 1-sample (paired) t-test to test Food Knowledge, Food Skill Master, and Dietary Behavior scores. We will construct 95% confidence intervals around the change separately for boys and girls, pooling them if we discern no important difference by sex. If, based on Aim #1, we believe that there were important implementation differences across the two waves, we will analyze them separately, acknowledging our power will be more limited.

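### The plan does not say that the TGMD-3 video coder is masked to time point; with one group and change tested against zero, any scoring shift goes straight into the result, and the recordings make this cheap to prevent

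*Combined protocol and SAP*

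**What the plan says.** All of the following comes from the combined protocol and SAP.

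- **How the test is given and scored (Section 10, part 3, Movement Skills).** "The TGMD-3 will be administered via Zoom (i.e., remotely) at baseline and post-12 weeks". "The TGMD-3 is a direct observation skill assessment with 3-5 performance criteria for each skill". Scoring is done from the recording: "A trained professional will review and code the video-recorded TGMD-3 performance on each skill and provide a score at baseline and post-test".
- **Help around the test (same place).** Instructional videos "will be provided to the participants and parents in advance for them to review and practice before the testing session", and a parent "may provide prompting and/or clarification to their child".
- **Analysis (Section 13, Specific Aim #2a).** The plan is to run "1-sample paired t-tests for change (against the null hypothesis of a change of zero) in separate tests for TGMD-3 scores", among other measures. "We will construct 95% confidence intervals around the measure of change separately for boys and girls"; the sexes are pooled if no important difference is seen.
- **Expectation and design (Section 4).** The team expects that "participants will show significant improvements in physical literacy and food literacy outcomes". Everyone receives the intervention, and a controlled study is named only as the next step.
- **Who does what.** Section 10 calls the person running the Zoom test a trained tester. The enrollment procedures in Section 11 use the term trained professional for that role, which is the term Section 10 uses for the coder. The text therefore leaves open whether tester and coder are the same person.
- **Timing (Section 9).** The timeline lists data coding as a late task, near or after post-intervention data collection. The table layout is broken and the row does not name the TGMD-3.

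No section describes masking to time point, scoring order, a second coder or a reliability check for the TGMD-3.

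**The concern.** Each TGMD-3 skill is credited criterion by criterion by a person watching a video. A coder who knows that a recording is the post-test, and who belongs to a team expecting improvement, may give the benefit of the doubt more often. A coder who scores all baselines first and all post-tests later may also drift in strictness for reasons unrelated to expectation. In a two-arm trial scored by the same process, much of this would cancel between arms. Here nothing cancels it.

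The TGMD-3 is the only measure of movement skill in Section 10 and one of the Aim 2a tests. Section 4 makes a larger controlled study the next step if this one succeeds. What is at stake is a preliminary efficacy signal that may partly reflect scoring, when the recordings needed to avoid this already exist.

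**Working it through.** **1. What the plan offers to work with.** There is no planned figure to reproduce on this point. The sample-size paragraph in Section 13 is built on a different motor test, the CAMSA, so its SDs of change (5.19 total, 3.10 skill) cannot be used to size a TGMD-3 scoring shift. The documents give no SD of TGMD-3 change and no coder reliability.

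**2. Effect on the estimate.** For participant *i*, write the observed change as

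D_i = (true change)_i + (coder leniency at post-test − coder leniency at baseline) + error_i.

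If the leniency difference has mean δ, then

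E(mean D) = mean true change + δ.

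The shift enters one-for-one. It does not depend on *n*, so more participants make the biased estimate more precise without reducing the bias.

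**3. Effect on the test (illustration).** Inputs:

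- Test: one-sample (paired) t-test against zero (Section 13).
- Alpha: 0.05 (Section 13). Sidedness is not stated; two-sided is assumed.
- *n*: 12 per sex (sample-size basis) and 15 per sex (enrolled); pooled, 24 and 30; also 27, which is 30 less the 10% dropout allowed for in Section 24.
- True change: 0.
- Shift: b = δ / SD of change, **assumed** to be 0.1, 0.2 or 0.3.

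The t statistic is then noncentral t with n − 1 degrees of freedom and noncentrality b√n. The chance of a significant *improvement* is

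P(T > t_{0.975, n−1}), with T ~ t(n − 1, b√n).

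Example: for n = 30 and b = 0.2, the noncentrality is 0.2 × √30 = 1.095, the critical value is 2.045, and the probability is 18.4%.

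| n | b = 0 | b = 0.1 | b = 0.2 | b = 0.3 |
|---|---|---|---|---|
| 12 (one sex) | 2.5% | 5.0% | 9.2% | 15.6% |
| 15 (one sex, no attrition) | 2.5% | 5.5% | 10.8% | 19.0% |
| 24 (pooled) | 2.5% | 6.8% | 15.4% | 29.1% |
| 27 (pooled, 10% dropout) | 2.5% | 7.2% | 16.9% | 32.3% |
| 30 (pooled, no attrition) | 2.5% | 7.6% | 18.4% | 35.5% |

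The pooled rows apply only if the sexes are combined.

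**4. Sensitivity to the framing.** Counting rejections in either direction, from a nominal 5%, the figures for b = 0.1 / 0.2 / 0.3 are 6.2 / 9.7 / 15.8% at n = 12 and 8.3 / 18.5 / 35.5% at n = 30. For a smaller shift of b = 0.05, the upper-tail chance is 3.6% at n = 12 and 4.5% at n = 30.

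**5. Effect of the remedy.** If masked, random-order scoring brings δ to zero, the upper-tail rate returns to 2.5%. No sample-size figure changes.

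**The case against.** - **The point rests on silence.** Section 10 calls its measure descriptions brief and refers to the grant application, which is not available here and may set out the coding procedure. Nothing says the coder knows the time point. This stands as a limit: the finding is that masking is not described, not that the coder is unmasked. If masking is already planned, one sentence in Section 10 settles the matter.
- **Coding may already happen late.** If the late coding task in Section 9 covers the TGMD-3 videos, both sets may be scored close together, which makes drift over calendar time less likely. That is fair, but it settles neither masking nor scoring order, and it also means that holding the recordings costs little.
- **The gain is partial.** Retest, advance practice, parent prompting and maturation all remain, and cues in the recording may reveal the time point. Efficacy is labelled preliminary and feasibility is the first aim. All true; this limits the weight of the point but is no reason to keep an avoidable source of bias.
- **The percentages show the arithmetic of an assumed bias.** They do, and the shift sizes have no anchor in the documents. The upper-tail framing also looks more dramatic at small shifts than the two-sided one. The case rests on the design, not on any one cell of the table.

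**Conclusion.** The concern holds as a cheap improvement that should be made. On the available text, an observer-rated score is compared with itself over time, without a control arm and without any stated protection against a scoring difference between time points. Such a difference would pass in full into the mean change, and the paired t-test could not tell it from a gain in skill.

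The size is unknown. Under assumed shifts of 0.1 to 0.3 SD of change and no true change, the chance of a false improvement would be 5.0% to 15.6% at n = 12 and 7.6% to 35.5% at n = 30, against 2.5% nominal. These figures assume a two-sided 5% test and normally distributed changes. Masking removes coder expectation and random order stops drift from lining up with time point. Neither makes the change attributable to the intervention.

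**What to change.** Add to Section 10, Movement Skills, wording such as:

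> TGMD-3 recordings will be held until post-testing is complete, labelled with a random code that shows neither date nor time point, and scored in random order by a coder masked to time point. Both recordings of a participant will be scored by the same coder. Where existing staffing allows, the coder will not have tested that participant or delivered sessions.

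Report how many recordings revealed their time point to the coder, since visual or spoken cues, including the tester's instructions and the parent's prompting, may make masking incomplete.

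**Cost.** Small but not zero: scoring waits until post-testing is finished, the files must be relabelled, and a random list must be drawn up and kept by someone other than the coder. There are no extra visits or participants. The documents do not show whether a separate coder would need more staff, so that part is conditional on existing staffing.
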